#### **7.1.2. Secondary Endpoints**

Secondary endpoints will include:

- Pharmacokinetic (PK) analyses
- Change (reduction) in influenza virus titer by  $\log_{10}$  TCID50/mL and by reverse transcriptase polymerase chain reaction (RT-PCR)
- Time to alleviation of clinical symptoms of influenza (per age appropriate symptoms).
- Time to resolution of fever
- Incidence of influenza-related complications
- Incidence of hospital admission post treatment
- Changes in viral shedding measured by quantitative viral titer assay (TCID50) and/or quantitative PCR
- Change in influenza virus susceptibility to neuraminidase inhibitors

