#### 13.8.2. Effectiveness Analyses

Time to resolution of fever, defined as a temperature  $< 99.4^{\circ}\text{F}$  oral with no antipyretic medications taken for at least 12 hours, will be estimated overall and by each age group using the method of Kaplan-Meier. Subjects who do not achieve resolution of fever will be censored at the time of their last assessment.

Time to resolution of influenza symptoms, defined as the time from initiation of study drug until the start of the 21.5-hour period (24 hours- 10%) where all symptoms of influenza are recorded as none or mild, will be estimated overall and for each age group using the method of Kaplan-Meier. Subjects who do not experience alleviation of symptoms will be censored at the time of the last non-missing symptom assessment.

Reduction in viral shedding will be assessed as the change from baseline in  $\log_{10}$  TCID50/mL and RT-PCR, and will be summarized overall, by age group, and by study visit.

Changes in virus susceptibility to neuraminidase inhibitors between virus cultured at Baseline and the last post-treatment sample from which virus can be cultured will be assessed using virology laboratory tests. Virology laboratory tests will include phenotypic characterizations of influenza virus recovered (hemagglutinin and neuraminidase) and viral susceptibility to peramivir, and genotypic analysis of primary virus isolates. These analyses will be presented overall, and separately by age group and viral subtype.

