5.2. EFFECTIVENESS ANALYSIS

5.2.1. Effectiveness Endpoints

The effectiveness endpoints include:

- Time to resolution of fever
- Time to alleviation of clinical symptoms of influenza
- Change (reduction) in influenza virus titer by \log_{10} TCID₅₀/mL
- Change (reduction) in influenza virus titer by RT-PCR results
- Changes in viral shedding measured by quantitative viral titer assay (TCID₅₀) and/or quantitative PCR.
- Change in influenza virus susceptibility to neuraminidase inhibitors
- Incidence of influenza-related complications as determined by investigator
- Incidence of hospitalization admission post treatment
- Usage of antipyretic medication
- Change in daily activities per the visual analog scale
- Time to resumption of usual daily activities per the visual analog scale

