5.2.2. Effectiveness Analyses

A subject's oral temperature taken by subjects and recorded in the diary by subjects/caregivers will be summarized by age group and overall by study visit. A subject has Resolution of Fever if he/she has an oral temperature $< 37.4^{\circ}\text{C}/99.4^{\circ}\text{F}$ oral and no antipyretic medications have been taken for at least 12 hours. The time to resolution of fever will be estimated for each age group and overall using the Kaplan-Meier method with temperature and symptom relief medication information obtained from the subject diary data. Subjects who do not have resolution of fever will be censored at the time of their last non-missing post-baseline temperature assessment.

Alleviation of symptoms will be determined by assessment of symptoms as reported on each Subject Diary. The time to alleviation of symptoms, defined as the time from initiation of study drug until the start of the 21.5 hour period (24 hours less 10%) where all symptoms of influenza are recorded as none or mild, will be estimated overall and for each age group using the Kaplan-Meier method. Subjects who do not experience alleviation of symptoms will be censored at the date of their last non-missing post-baseline assessment.

Change from baseline in \log_{10} TCID₅₀/mL through Day 3, Day 7, and Day 14 will be presented by age group and overall for subjects with positive viral titers at baseline (\log_{10} TCID₅₀/mL > 0.5). A box plot and a histogram of the TCID₅₀/mL values will be presented by visit and age group. In addition, the median change from baseline in TCID₅₀/mL will be presented by visit and age group.

The number and percent of subjects with positive viral titers at baseline (\log_{10} TCID₅₀/mL > 0.5) that shed virus at each visit will be presented by age group and overall.

The RT-PCR results at each visit will be presented by age group and overall for subjects with positive RT-PCR results at baseline.

Change from baseline to last positive value of influenza virus susceptibility to neuraminidase inhibitors will be assessed using virology laboratory tests. Virology laboratory tests will include phenotypic characterizations of influenza virus recovered (hemagglutinin and neuraminidase) and viral susceptibility to zanamivir, oseltamivir, and peramivir, as well as genotyping of virus isolates. These analyses will be presented overall and by age group and viral subtype.

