6. CHANGES IN THE PLANNED ANALYSES

An analysis of the number of doses of antipyretic medications will be prepared.

There are no further changes anticipated to the protocol specified analyses. Should any more deviations occur, these changes will be fully described in the Clinical and Statistical Report.

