Figure 14.2.3.4	Median (with IQR) Change from Baseline Viral Titers (TCID ₅₀ /mL) by Study Visit: Subjects with Positive Baseline Titers: Intent-to-Treat Infected Population
Table 14.2.4.1	Summary of Viral Shedding by Study Visit; Subjects with Positive Baseline Titers: Intent-to-Treat Infected Population
Table 14.2.4.1.X	Summary of Viral Shedding by Study Visit: Subjects with Positive Baseline Titers: Viral Subtype: Intent-to-Treat Infected Population
Table 14.2.5.1	Summary of RT-PCR Result by Study Visit: Subjects with Positive Baseline RT-PCR: Intent-to-Treat Infected Population
Table 14.2.5.1.X	Summary of RT-PCR Result by Study Visit: Subjects with Positive Baseline RT-PCR: Viral Subtype: Intent-to-Treat Infected Population

Output Number	Output Title
Table 14.2.6	Change of Influenza Virus Susceptibility to Neuraminidase Inhibitors: Intent-to-Treat Infected Population
Table 14.2.7	Summary of Influenza-Related Complications and Hospitalizations: Intent-to-Treat Infected Population
Table 14.2.8	Number of Doses of Antipyretic Medications: Intent-to-Treat Infected Population
Table 14.2.9.1	Summary of Subject-Rated Assessment of Ability to Perform Daily Activities: Intent-to-Treat Infected Population
Table 14.2.9.2	Time to Return to Usual Activities: Intent-to-Treat Infected Population
Table 14.3.1.1	Overall Summary of Treatment-Emergent Adverse Events: Safety Population
Table 14.3.1.2	Treatment-Emergent Adverse Events by System Organ Classification, Preferred Term and Greatest Severity: Safety Population
Table 14.3.1.3	Treatment-Emergent Adverse Events by System Organ Classification and Preferred Term: Safety Population
Table 14.3.1.4	Treatment-Emergent Adverse Events Possibly, Probably, or Definitely Related to Study Drug by System Organ Classification and Preferred Term: Safety Population
Table 14.3.1.5	Treatment-Emergent Serious Adverse Events by System Organ Classification and Preferred Term: Safety Population
Table 14.3.1.6	Treatment-Emergent Adverse Events Leading to the Discontinuation of Study by System Organ Classification and Preferred Term: Safety Population
Table 14.3.1.7	Treatment-Emergent Adverse Events Leading to the Discontinuation of Study Drug by System Organ Classification and Preferred Term: Safety Population
Table 14.3.1.8	Treatment-Emergent Adverse Events Occurring in $\geq 10\%$ of Subjects by Preferred Term: Safety Population

Output Number	Output Title

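### The protocol plans change from baseline in RT-PCR, but the SAP specifies only RT-PCR results by visit and does not declare the departure

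*SAP*

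**What the plan says.** Protocol 7.1.2 lists as a secondary endpoint "Change (reduction) in influenza virus titer by" log10 TCID50/mL and, in the same bullet, by RT-PCR. Protocol 13.8.2 gives the method: "Reduction in viral shedding will be assessed as the change from baseline in" log10 TCID50/mL "and RT-PCR, and will be summarized overall, by age group, and by study visit". SAP 5.2.1 separates the two measures and keeps the second as its own bullet: "Change (reduction) in influenza virus titer by RT-PCR results".

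SAP 5.2.2 plans change from baseline for TCID50 at Days 3, 7 and 14, in subjects with baseline log10 TCID50/mL above 0.5. For RT-PCR its one sentence is: "The RT-PCR results at each visit will be presented by age group and overall for subjects with positive RT-PCR results at baseline". The matching output, Table 14.2.5.1, is titled "Summary of RT-PCR Result by Study Visit: Subjects with Positive Baseline RT-PCR: Intent-to-Treat Infected Population", and Table 14.2.5.1.X repeats it by viral subtype.

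SAP Section 6 names one change, an added analysis of antipyretic doses, and continues: "There are no further changes anticipated to the protocol specified analyses". SAP 5.4 states that the SAP prevails where it differs from the protocol.

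**The concern.** The endpoint is a change, and the scheduled analysis is a set of visit-by-visit results. A programmer who follows SAP 5.2.2 and the Section 9 output list would produce no RT-PCR change from baseline, although the protocol promises one.

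The gap matters because of who is left out. The ITTI population is defined by PCR, while the TCID50 change analysis needs a positive culture titre at baseline. RT-PCR is the measure that could describe viral-load change in PCR-positive subjects whose culture titre does not pass the threshold. Without it, the reported viral decline describes only the culture-positive part of the infected population.

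**Working it through.** No arithmetic applies: the documents give no figure for this endpoint, and the study is descriptive. The check traces the two viral measures through both documents.

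| Step | TCID50 | RT-PCR |
|---|---|---|
| Endpoint (Protocol 7.1.2, SAP 5.2.1) | Change | Change |
| Method in Protocol 13.8.2 | Change from baseline | Change from baseline |
| Transformation (SAP 3.3.7) | log10 | None stated |
| Method in SAP 5.2.2 | Change from baseline | Results at each visit |
| Subjects in SAP 5.2.2 | Baseline log10 titre > 0.5 | Baseline RT-PCR positive |
| Summaries of change in SAP Section 9 | Tables 14.2.3.1 and 14.2.3.1.X, Figure 14.2.3.4 | None |
| Other outputs for the RT-PCR endpoint | – | Tables 14.2.5.1 and 14.2.5.1.X (results) |

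So TCID50 has three summaries of change and RT-PCR has none. The exposure-response scatter plot of viral change (Figure 14.4.3) also uses TCID50, according to SAP 5.2.3. It is a plot against plasma concentration and does not summarise change by visit.

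**Could another part of the plan fill the gap?**

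- SAP 3.3.8 defines change from baseline in general terms but attaches no RT-PCR output to it.
- SAP Section 1 says virology will be reported separately, but also that the SAP describes all virology analyses. The separate report therefore does not supply the missing specification.
- The option of TCID50 and/or quantitative PCR belongs to a separate viral-shedding bullet in Protocol 7.1.2 and SAP 5.2.1. It does not remove the change-by-RT-PCR bullet.

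**Can the change be read from results by visit?** If the results are positive or negative, the table shows conversion, which is not a change in titre. If they are quantitative, a difference between visit medians is not the median within-subject change. A difference between visit means equals the mean change only when the same subjects contribute at both visits. In neither case can the spread of the change be recovered.

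**Are the data planned?** Yes. Protocol 10.1.2.1 and 10.1.2.3 to 10.1.2.5 specify a quantitative PCR assay on the baseline, Day 3, Day 7 and Day 14 swabs. Day 14 carries a conflict. Protocol 10.1, 10.1.2.5 and 10.3 and SAP 1.1 call for a swab that day, while the schedules of assessments (Protocol Table 1, SAP 1.2) mark virology swabs at Baseline, Day 3, Day 7 and Early Withdrawal only.

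**The case against.** The best defence is that this is missing detail and not a contradiction. Table 14.2.5.1 keeps a fixed baseline-positive group, so it would show conversion to negative or falling values over time. Table shells are not in the documents, and a change column may exist. The statement in SAP Section 6 could mean that the protocol's analysis still stands. PCR-positive, culture-negative subjects are not lost, because those who are PCR-positive at baseline appear in Table 14.2.5.1.

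Much of this limits the point. Three stronger readings are tempting, and the documents do not support them.

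- A reader might infer that the endpoint will not be delivered. Without the shells, the documents show only that the change is not specified.
- A reader might infer that the endpoint is defined as quantitative RT-PCR. The change bullets and Protocol 13.8.2 say only RT-PCR. The word quantitative comes from the shedding bullet and the swab procedures.
- A reader might want to say what fraction of the ITTI population is affected. Nothing in either document gives the culture-negative share.

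The core still stands. Protocol 13.8.2 names change from baseline in RT-PCR. The SAP keeps the endpoint, specifies a different summary for it, and does not list the difference. If the protocol's analysis is meant to stand, no output in Section 9 is assigned to it.

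**Conclusion.** The SAP does not specify the RT-PCR change analysis that Protocol 13.8.2 plans and that its own Section 5.2.1 lists, and the departure is undeclared. As written, within-subject viral-load change is summarised only for subjects with baseline log10 TCID50/mL above 0.5. PCR-positive subjects at or below that value have no change summary. Their number is unknown from the documents.

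The consequence is limited to the completeness of one descriptive secondary endpoint in a single-arm study without hypothesis tests. No error rate is involved, and the primary safety endpoint is unaffected. The conclusion assumes that the Section 9 titles and the SAP 5.2.2 text describe the outputs fully. A table shell with a change column would reduce the point to a wording correction.

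**What to change.** In SAP 5.2.2 and Table 14.2.5.1 (with 14.2.5.1.X), add change from baseline in the quantitative RT-PCR result at each post-baseline swab visit, overall, by age group and by viral subtype, for subjects who are PCR-positive at baseline. Retitle the tables to match. Two details must be settled first:

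- **Unit and scale.** State the assay's reported unit. Use log10 if it is a concentration, and leave it untransformed if it is a cycle threshold. Amend SAP 3.3.7 accordingly.
- **Values below quantification.** State a rule. Otherwise subjects who clear virus may have no computable change, and SAP 3.3.4 imputes nothing beyond the cases that it lists.

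The Day 14 swab text and the schedules of assessments must be reconciled to decide whether Day 14 is included. The same conflict affects the Day 14 TCID50 change already planned.

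If the sponsor prefers not to add the analysis, SAP Section 6 should declare and justify its omission. The added table will not cover every ITTI subject, because SAP 3.3.8 confirms influenza from any positive specimen during the study and some subjects may be PCR-negative at baseline.

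The cost is one extra descriptive table and a small amount of programming. The assay is already planned.

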**Effectiveness:**

Clinical:

- Time to alleviation of clinical influenza symptoms
- Time to resolution of fever
- Time to resumption of usual activities
- Incidence of influenza-related hospitalizations
- Incidence of hospital admission (for any reason) post treatment

Virologic:

- Changes in viral shedding measured by quantitative viral titer assay (TCID50) and/or quantitative polymerase chain reaction (PCR)
- Change in influenza virus susceptibility to neuraminidase inhibitors

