#### 11.1.1. Definitions

##### 11.1.1.1. Adverse Event

An AE is any untoward medical occurrence in a clinical study subject. No causal relationship with the study drug or with the clinical study itself is implied. An AE may be an unfavorable and unintended sign, symptom, syndrome, or illness that develops or worsens during the clinical study. Clinically relevant abnormal results of diagnostic procedures including abnormal laboratory findings (e.g., requiring unscheduled diagnostic procedures or treatment measures, or resulting in withdrawal from the study) are considered to be AEs.

Surgical procedures are not AEs but may constitute therapeutic measures for conditions that require surgery. The condition for which the surgery is required is an AE, if it occurs or is detected during the study period. Planned surgical measures permitted by the clinical study protocol and the condition(s) leading to these measures are not AEs, if the condition(s) was (were) known before the start of study treatment. In the latter case the condition should be reported as medical history.

Assessment of influenza symptoms will be documented and analyzed as a measure of effectiveness of the study treatment. These symptoms will not be reported as AEs unless the symptom(s) worsen to the extent that the outcome fulfills the definition of an SAE, which then must be recorded as such.

AEs are designated as “non-serious” or “serious.”

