##### 11.1.1.2. Serious Adverse Event

An SAE is an adverse event that results in any of the following outcomes:

- Death
- Is life-threatening (subject is at immediate risk of death at the time of the event; it does not refer to an event that hypothetically might have caused death if it were more severe)
- Requires in-subject hospitalization (formal admission to a hospital for medical reasons) or prolongation of existing hospitalization

- Results in persistent or significant disability/incapacity (i.e., there is a substantial disruption of a person's ability to carry out normal life functions)
- Is a congenital anomaly/birth defect

Important medical events that may not result in death, are not life-threatening, or do not require hospitalization may be considered an SAE when, based upon appropriate medical judgment, they may jeopardize the subject or may require medical or surgical intervention to prevent one of the outcomes listed in this definition. Examples of such events include allergic bronchospasm requiring intensive treatment in an emergency room or at home, blood dyscrasias or convulsions that do not result in subject hospitalization, or the development of drug dependency or drug abuse.

Hospitalization, as per the institution's standard of care (SOC) to treat influenza in elderly patients is not considered an SAE and should not be reported as such. Any adverse event that causes a prolongation of an existing hospitalization must be reported as per [Section 11.1.5](#).

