The development of any post treatment genotypic changes in neuraminidase and hemagglutinin will be assessed by comparison of sequences from baseline and last positive post-treatment virus samples. These analyses will be presented overall and by age group and viral subtype.

The number and percentage of subjects experiencing influenza related complications will be summarized by age group and overall by complication MedDRA version 18.0 preferred term.

The number and percentage of subjects who are hospitalized due to any TEAE and due to any TEAE related to study drug after initiation of treatment will be summarized by age group and overall.

The number of doses of antipyretic medications, as recorded in the subject diary, taken throughout the study and by study day will be summarized by age group and overall.

The change in daily activities will be summarized each day by age group and overall. The ability to perform usual activities is defined as a subject rating of 10 (able to perform all usual activities fully) on the visual analog scale the subject uses to rate his or her current ability to perform usual activities compared with normal ability. The time to return to usual activities will be estimated for each age group and overall using the Kaplan-Meier method. Subjects who do not return to normal activities will be censored at the time of their last non-missing post-baseline assessment.

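### The SAP lists post-treatment hospital admission with no limit by cause, but its only analysis rule counts admissions caused by TEAEs

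*SAP*

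**What the plan says.** The endpoint appears in three places:

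- Protocol synopsis, criteria for evaluation: "Incidence of hospital admission (for any reason) post treatment", and as a separate item "Incidence of influenza-related hospitalizations".
- Protocol 7.1.2: "Incidence of hospital admission post treatment".
- SAP 5.2.1: "Incidence of hospitalization admission post treatment".

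The only analysis rule is in SAP 5.2.2. It asks for a count with its percentage, within each age group and in total, for this set: "subjects who are hospitalized due to any TEAE and due to any TEAE related to study drug after initiation of treatment". The output is Table 14.2.7, on the ITTI population; its title covers complications and hospitalizations without mentioning TEAEs.

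The protocol has no detailed hospitalization analysis. Section 13.8.1 says only that every effectiveness endpoint is summarized descriptively. SAP section 6 declares one change, a count of antipyretic doses, and expects no others.

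**The concern.** The endpoint concerns whether a subject is admitted after treatment. The analysis rule concerns whether a subject is admitted because of a treatment-emergent adverse event. The two agree only if every post-treatment admission has a TEAE behind it, and the protocol's adverse event definitions do not guarantee that.

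At stake is the meaning of one reported rate. Followed as written, the plan specifies no any-cause rate, and its count can fall short of the endpoint the SAP itself lists. Because the title of Table 14.2.7 has no TEAE qualifier, a reader could take the TEAE-driven figure for all admissions.

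**Working it through.** No figure in the plan needs reproducing: the documents give no admission rate, target or sample-size basis for this endpoint. The check compares the endpoint with the rule, type of admission by type of admission.

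**Step 1: what becomes a TEAE.** SAP 3.3.8 treats an event reported on the CRF as treatment-emergent if it occurs from the start of study drug to 14 days after the last dose. An admission is therefore counted only if an adverse event is reported behind it.

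**Step 2: which post-dose admissions have one.**

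| Admission starting after dosing | Reported as an AE? | In the listed endpoint? | In the 5.2.2 count? |
|---|---|---|---|
| New medical event unrelated to influenza | Yes, as an SAE, because hospitalization is a seriousness criterion (protocol 11.1.1.2) | Yes | Yes |
| Influenza symptoms or complications, outside standard-of-care hospitalization | Yes, once SAE criteria are met (protocol 11 and 11.1.1.1) | Yes | Yes |
| Standard-of-care influenza admission of an elderly subject | No | Yes | No |
| Protocol-permitted planned surgery for a condition known before treatment | No | Yes | No |

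The third row follows from two rules read together. On influenza symptoms, protocol 11.1.1.1 says: "These symptoms will not be reported as AEs unless the symptom(s) worsen to the extent that the outcome fulfills the definition of an SAE". Protocol 11.1.1.2 then says: "Hospitalization, as per the institution's standard of care (SOC) to treat influenza in elderly patients is not considered an SAE". Such an admission meets neither test, so no TEAE is recorded for it.

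The fourth row follows from protocol 11.1.1.1: "Planned surgical measures permitted by the clinical study protocol and the condition(s) leading to these measures are not AEs", provided the condition was known before study treatment.

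**Step 3: whether other outputs fill the gap.** SAP section 5 promises that all collected data will be listed, so individual admissions may still appear. However, no listing in SAP section 9 is titled for hospital admissions, and the SAE listing would not show an admission that is not an SAE. A listing also does not give an incidence.

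**Step 4: the influenza-related endpoint.** No summary row identifies admissions as influenza-related. Those that are SAEs can be partly traced by preferred term in Table 14.3.1.5 and in the listings. This endpoint appears only in the synopsis, not in protocol 7.1.2, so it is first an inconsistency within the protocol.

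**Step 5: size per missed admission.** With *n* ITTI subjects, one missed admission lowers the reported percentage by 100/*n* points. If all planned subjects are PCR-confirmed:

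- overall, *n* = 120: 100/120 = 0.83 percentage points;
- elderly, at the planned minimum of *n* = 80: 100/80 = 1.25 percentage points.

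The step grows as fewer subjects are PCR-confirmed. No number of missed admissions is assumed.

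**The case against.** The strongest reply is that the gap is narrow. Hospitalization is itself an SAE criterion, so a TEAE-driven count already takes in nearly every unplanned post-dose admission. That is correct, and it limits the concern to the last two rows of the table.

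Those two rows may also be close to empty. Protocol 8.2 treats standard-of-care hospitalization as an eligibility matter, and Table 1 expects screening and dosing on the same date, so many such stays may begin before the infusion and not be post-treatment at all. The surgery exemption covers only measures the protocol permits, and follow-up lasts about 14 days, so that case is largely theoretical. Both points stand as limits on size. They do not rule out admission after dosing, since nothing in the protocol requires admission to come first.

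It can also be said that a SAP may make a brief endpoint operational, and that SAP 5.4 lets the SAP override the protocol. That does not settle the matter, because 5.2.1 and 5.2.2 disagree within the SAP. The complaint about section 6 is weaker: the protocol specified no detailed hospitalization analysis to depart from, only the general commitment in 13.8.1.

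Finally, the data may not support an any-cause count. Protocol 10.2.5 says further information on any admission will be collected but not what it contains, and it points to SAE reporting. The schedule of assessments has no hospitalization item. This stands, and the fix has to allow for it. The table shell is also not in the documents, so its row labels might make the restriction clear.

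**Conclusion.** The concern holds. As written, the only analysis rule measures something narrower than the endpoint in SAP 5.2.1, protocol 7.1.2 and the synopsis, and the narrowing is not declared. The case that matters is the post-dose standard-of-care influenza admission of an elderly subject, in a study planned to enrol at least 80 elderly among about 120.

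Confidence is high on the mismatch of definitions. The size of any undercount is unknown and may be zero; it depends on how many such admissions begin after dosing. The figures of 0.83 and 1.25 points are the weight of one subject under full PCR confirmation, not an estimate of bias. The study is single-arm, descriptive and without hypothesis tests, and its primary safety objective is not affected. The wording should be corrected, but no main conclusion of the trial depends on it.

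**What to change.** In SAP 5.2.2 and Table 14.2.7, make the summary match the endpoint. Suggested wording:

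> For each age group and overall, the count and percentage of subjects with a hospital admission of any cause that begins after study drug is started will be presented.

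Use the admission data collected under protocol 10.2.5. Where those data allow, add rows for influenza-related and for standard-of-care admissions, so that the part of the elderly rate that reflects site practice is visible. Keep the TEAE and drug-related counts, labelled as a safety summary.

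In SAP section 6, state any departure from the listed endpoint, any limit of the collected data, and how the influenza-related endpoint found only in the synopsis is handled. If admissions that were not SAEs were not captured, say that only TEAE-driven admissions can be counted, and label the table accordingly.

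The cost is wording in two SAP sections and one revised table, with no new visit or procedure. The any-cause count and the extra rows depend on whether non-SAE admissions, their start times and their causes were recorded. The drawback is an elderly admission rate that partly reflects institutional practice.
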